#### 7.1.1.1 Screen failures

Patients who sign an ICF but fail to undergo a biopsy (or provide archival tissue) or are otherwise found to be ineligible after signing the study ICF will be considered screen failures for this protocol. Patients identified as screen failures under the treatment protocol CLEE011A2404 will not be enrolled under this protocol.

### 7.1.2 Patient data to be collected in the central laboratory requisition forms

Data for this companion sample collection protocol will be collected via the central laboratory requisition forms completed for each sample. These requisition forms will document that informed consent has been obtained for participation in this protocol and for storage of biological samples, confirm that the patient met the inclusion/exclusion criteria for CLEE011A2404, and collect information about the lesions biopsied at baseline and upon progression [REDACTED]. Any adverse events considered by the investigator to be related to the biopsy procedure, should be captured in the CLEE011A2404 study EDC database, with a comment that it is related to the US companion

sample collection protocol CLEE011AUS42. Additional data collected as part of the CLEE011A2404 protocol and needed for the interpretation of the results from the genomic analyses, will also be utilized.

### **7.1.3 Early study termination, and premature withdrawal**

#### **7.1.3.1 Early study termination**

This study can be terminated at any time for any reason by Novartis. The investigator will be responsible for informing IRBs of the termination of this study

#### **7.1.3.2 Premature withdrawal**

Patients may voluntarily withdraw from either the CLEE011A2404 and/or this study CLEE011AUS42 or be dropped from it at the discretion of the investigator at any time. The reason for discontinuation will be recorded on the applicable corresponding eCRFs in the CLEE011A2404 EDC database (if patient is withdrawn from the CLEE011A2404 study) and captured on the central laboratory requisition form for US companion sample collection protocol CLEE011AUS42.

If a patient withdraws consent, Novartis will continue to retain and use all research results that have already been collected for the study evaluation. All biological samples that have already been collected may be retained and analyzed at a later date.

If a patient withdraws from the CLEE011A2404 study, the investigator will still receive the output of the data collected from this study up to the time point of the patient's withdrawal.

If a patient withdraws consent, the investigator must make every effort (e.g. telephone, e-mail, letter) to determine the primary reason for this decision and record this information. Study treatment must be discontinued and no further assessments conducted.

## **7.2 Assessment**

### **7.2.1 Assessments in tumor tissue**

[figure not shown]
The tumor sample collections for this study are summarized in [Table 7-2](#).

All assessments will be performed by a Novartis designated central laboratory. Instructions for collection, preparation and shipment can be found in the laboratory manual. Required sample collection information must be entered on the appropriate requisition forms provided by the central laboratory.

Tumor samples will be taken pre-treatment (during screening, with an allowed one month window from C1D1 if unable to obtain during screening), and following progression. Blocks are preferred but if not possible, 20 unstained slides (minimum 15) should be made available for biomarker studies. If a tumor sample is not accessible pre-treatment, an archival sample is allowed (metastatic site preferred). A pathology report must be submitted along with the patient's archival tumor block/slides. Biopsy collection will also be performed at the time of disease progression (and prior to the start of subsequent treatment) for identifying potential markers of lack of response/resistance.

[figure not shown]
Tumor samples will be tested for genetic and proteomic alterations (e.g., gene expression, mutations, amplifications, deletions and/or protein expression/activation etc.) that are involved in the D-cyclin-CDK4/6-INK4a-Rb and mTOR pathways, such as mutations of CCND1, PIK3CA, PTEN and CDK4, gene amplification of CCND1 and CDK4, deletion of CDKN2A, as well as potential resistant/escape pathways to CDK 4/ 6 inhibitors. Other cancer associated genes will also be investigated in the tumor tissue from all patients, with the intention of understanding potential mechanisms of resistance to prior CDK 4/6 inhibitors. Biomarker analyses will be correlated with clinical outcome to determine potential predictive biomarkers of ribociclib/letrozole response and resistance.

When choosing lesions for biopsy after the development of resistance, a sample from the same lesion chosen at screening/baseline is preferred if the lesion is growing in size, can be identified, and remains accessible to safely biopsy. Detailed instructions for the collection, handling, and shipping of biomarker samples are outlined in the Laboratory Manual.

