## Glossary of terms

Assessment	A procedure used to generate data required by the study
Biologic Samples	A biological specimen including, for example, blood (plasma, serum), saliva, tissue, urine, stool, etc. taken from a study subject or study patient
Control drug	A study treatment used as a comparator to reduce assessment bias, preserve blinding of investigational drug, assess internal study validity, and/or evaluate comparative effects of the investigational drug
Cohort	A group of newly enrolled patients treated at a specific dose and regimen (i.e. treatment group) at the same time
Cycles	Number and timing or recommended repetitions of therapy are usually expressed as number of days (e.g.: q28 days)
Dose level	The dose of drug given to the patient (total daily or weekly etc.)
Enrollment	Point/time of patient entry into the study; the point at which informed consent must be obtained (i.e. prior to starting any of the procedures described in the protocol)
Investigational drug	The study treatment whose properties are being tested in the study; this definition is consistent with US CFR 21 Section 312.3 and is synonymous with "investigational new drug."
Investigational treatment	Drug whose properties are being tested in the study as well as their associated placebo and active treatment controls (when applicable). This also includes approved drugs used outside of their indication/approved dosage, or that are tested in a fixed combination. Investigational treatment generally does not include other study treatments administered as concomitant background therapy required or allowed by the protocol when used in within approved indication/dosage
Medication number	A unique identifier on the label of each study treatment package which is linked to one of the treatment groups of a study
Other study treatment	Any drug administered to the patient as part of the required study procedures that was not included in the investigational treatment
Subject Number	A unique identifying number assigned to each patient/subject/healthy volunteer who enrolls in the study
Randomization number	A unique treatment identification code assigned to each randomized patient, corresponding to a specific treatment arm assignment
Stage related to study timeline	A major subdivision of the study timeline; begins and ends with major study milestones such as enrollment, randomization, completion of treatment, etc.

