	
The baseline/screening tumor sample (metastatic site preferred) should be obtained during the screening process for the CLEE011A2404 study prior to starting the investigational drug regimen. However, a window of one month into study treatment will be permitted if not possible to obtain a fresh tumor tissue sample during the screening period so as to not delay study treatment. If fresh tissue is unavailable, archival tissue from the primary or metastatic site (metastatic site preferred) will then be acceptable (and may be sent in after the start of study treatment to allow for logistic planning of obtaining the archival sample). The second tumor tissue sample will be obtained at time of progression and prior to subsequent therapy.
 
Population	Patients enrolled in the United States to protocol CLEE011A2404 (a study that includes men and postmenopausal women with HR+, HER2-aBC who had not received any prior hormonal agent for treatment of advanced disease).
Key Inclusion criteria	Patients eligible for this companion sample collection protocol sample collection protocol must meet all inclusion in CLEE011A2404.
Key Exclusion criteria	Patients eligible for this companion sample collection protocol must not meet any of the exclusion criteria in the CLEE011A2404 study, in addition to the following: 1. Patients without either fresh or archival tumor tissue accessible.
Investigational and reference therapy	Ribociclib 600mg oral daily (3 weeks on/ 1 week off) in combination with letrozole 2.5 mg oral once daily
Statistical methods	Details of the analyses including primary analysis to be will be described in a corresponding statistical analysis plan.

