## 2.2 Rationale for study design

Tumor tissue samples will be collected in this trial at baseline to identify biomarkers that may be predictive of benefit from the combination of ribociclib and letrozole, understand the mutations present in newly diagnosed advanced breast cancer patients and to understand the heterogeneity of mutations across diverse patient populations. Tumor samples will also be collected at time of progression (End of Treatment). This will be done using both Nanostring and multiplexed approaches (Next Gen Sequencing) of but not limited to CCND1, CDKN2A, PIK3CA and PTEN as well as protein expression profiling of PDL-1 and CD8 using AQUA (Automated Quantitative Analysis), a fluorescent IHC. The biopsy collected at progression/end of treatment will be dedicated to understanding resistance to treatment of ribociclib in combination with letrozole as well as immune profiling of this patient population. This study also provides a unique opportunity to investigate the various mutations in a heterogeneous patient population with HR+/HER2- advanced breast cancer at initial diagnosis and following progression to CDK4/6 inhibition.

[figure not shown]
Tumor samples will be requested at baseline and following progression. Tumor tissue samples will be obtained only from patients who consent to participating in this sample tumor collection and will be sent to a third party central laboratory for analysis. All sites that participate in this study will receive the results of the genetic mutation of their patients' tumor tissue profile upon progression.

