### **4.1 Description of study design**

This is a multicenter, US specific, non-treatment based companion sample collection protocol. This protocol will evaluate the aberrations of common pathways for newly diagnosed HR+/HER2- advanced breast cancer tumors and responses to ribociclib in diverse patient populations. This companion sample collection protocol is available for all US patients enrolled on CLEE011A2404 (CompLEEment-1) and will not alter the planned treatment. Tumor collection required for this study will occur at two time points: at baseline/screening and upon the development of progressive disease as shown in [Section 7.2](#). For each tumor tissue sample, three analyses will be conducted (1), using Next Generation Sequencing (NGS): evaluating known human cancer-related genes to assess for genetic alterations and (2) Gene expression analysis using nanostring technology and (3) Protein assessment of PDL-1 and CD8 to evaluate the immune profile of this patient population pre and post-treatment to ribociclib.

[figure not shown]

The analyses of samples will be conducted in an on-going fashion as tumor tissue from patients becomes available. Sites will be provided with the results of the genetic mutation profiles of their patients' tumor upon progression.

The baseline/screening tumor sample (metastatic site preferred) should be obtained during the screening process for the CLEE011A2404 study prior to starting the investigational drug regimen. However, a window of one month into study treatment will be permitted if not possible to obtain a fresh tumor tissue sample during the screening period so as to not delay study treatment. If fresh tissue is unavailable, archival tissue from the primary or metastatic site (metastatic site preferred) will then be acceptable (and may be sent in after the start of study treatment to allow for logistic planning of obtaining the archival sample). The second tumor tissue sample will be obtained at time of progression and prior to subsequent therapy.

**Figure 4-1** Study design

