**Table 7-1 Visit evaluation schedule**

Visit Name	Protocol Section	Screening	Cycle 1	Cycle 6	Cycle 12	End of Treatment/Progression of Disease

Visit Name	Protocol Section	Screening	Cycle 1	Cycle 6	Cycle 12	End of Treatment/Progression of Disease
Day of Cycle		-21 to 1	1	1	1	within 15 days from the last dose
Obtain Informed Consent	7.1.1	X				
Tissue collection	7.2.1 7.2.3 7.2.4	X 				X

 Tissue sample may be obtained after 15 days if not feasible within 15 days from the last dose. Must be collected prior to starting subsequent therapy.

 If not collected during screening, can be collected during the first month of treatment. If fresh tissue sample cannot be obtained, archival sample may be sent in during the first month of treatment.

■ [REDACTED]

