**Table 7-2 Biomarker collection schedule**

Sample Type	Volume	Visit	Sample Collection
Baseline tumor biopsy (Fresh tissue from metastatic site preferred. If fresh tumor is not accessible, archival tissue will be accepted)	Blocks are preferred but if not possible, 20 unstained slides (minimum 15) should be made available.	Screening	Prior to treatment (or within the first month of study). If archival, can be sent in when obtained from sample storage.
Newly obtained post-progression tumor samples)	Blocks are preferred but if not possible, 20 unstained slides (minimum 15) should be made available.	Post- progression	Upon progression (prior to subsequent treatment)

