## **10 Statistical methods and data analysis**

This companion sample collection protocol seeks to explore the mechanisms of resistance to cancer treatment through the analysis of data from tumor samples at baseline and after development of disease progression, [REDACTED]

[REDACTED] Analyses are considered exploratory in nature and the detailed data analysis plan(s) will be described in stand-alone documents or, where appropriate, in the individual Statistical Analysis Plan (SAP) from corresponding parent treatment studies for inclusion in the respective CSRs.

Broadly, data analyses will seek to (1). analyze mutations present at the initial diagnosis of HR+/HER2- advanced breast cancer across diverse ethnicities (2). characterize the mutations identified at progression of disease following the treatment of ribociclib + letrozole and (3). characterize the immune response to ribociclib + letrozole. Descriptive statistics and exploratory modeling will be used. Details will be described in the data analysis plans.

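### Fresh tissue taken up to one month into treatment is classed as pre-treatment, and no visible rule separates it from untreated tissue in the exploratory expression and PDL-1/CD8 analyses

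*Combined protocol and SAP*

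**What the plan says.** The Synopsis and Section 4.1 ask for the baseline sample during screening, before study drug. If fresh tissue cannot be obtained by then, "a window of one month into study treatment will be permitted", so that treatment is not delayed. Archival tissue is accepted if fresh tissue is unavailable, and it may be shipped after treatment has begun.

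Three places carry this window into the label of the sample:

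- Section 7.2.1 puts it inside the definition: "Tumor samples will be taken pre-treatment (during screening, with an allowed one month window from C1D1 if unable to obtain during screening".
- Table 7-2 has one row for the baseline biopsy, with the visit given as Screening and the timing as "Prior to treatment (or within the first month of study".
- Table 7-1 marks tissue collection under Screening, not Cycle 1, and adds in footnote 2: "If not collected during screening, can be collected during the first month of treatment".

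The baseline tissue then has several uses. Section 4.1 plans gene expression on each sample, and "Protein assessment of PDL-1 and CD8 to evaluate the immune profile of this patient population pre and post-treatment to ribociclib". Section 10 aims to "characterize the immune response to ribociclib + letrozole". Section 2.2 says: "Tumor tissue samples will be collected in this trial at baseline to identify biomarkers that may be predictive of benefit". Section 7.2.1 adds that biomarkers will be correlated with clinical outcome.

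Section 10.1 admits to the biomarker analysis set any US patient in the parent study's full analysis set who has an evaluable biomarker assessment. It sets no condition on when the sample was taken. Sections 10 and 10.3 call the analyses exploratory and leave the detail to a SAP or stand-alone plans.

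**The concern.** In a pre/post comparison the pre sample stands for the tumour before any drug effect. Gene expression and protein levels can change with drug exposure, so tissue taken after weeks of ribociclib and letrozole need not measure that state. Analysed under the label the protocol gives it, such tissue sits on the untreated side of the contrast. It can then make the change look smaller or larger than it was.

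The predictor analysis has a related problem. A marker measured after dosing may partly reflect an early response to the drugs. Correlated with outcome, it could pass for a baseline predictor although it was not available before treatment.

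The window itself is an open and reasonable trade-off and is not at issue. The issue is the classification of the samples it yields. It concerns gene expression and PDL-1/CD8 protein. The primary and secondary endpoints in Section 3 are mutations, and the point does not extend to them.

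**Working it through.** The plan gives no sample size, power or other figure on this point, so there is nothing to reproduce. Two things can be checked: how much drug a window sample may have seen, and whether any visible text sets such samples apart.

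**1. Exposure at sampling**

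Inputs: ribociclib 600 mg daily, 3 weeks on and 1 week off, with daily letrozole (Synopsis); window of one month from C1D1 (Section 7.2.1). Assumptions: C1D1 is Day 1, dosing is uninterrupted, and a month is 28 to 31 days, because the protocol does not define it in days.

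For sampling on Day D, counting that day's dose:

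- ribociclib = D for D up to 21; 21 for D = 22 to 28; 21 + (D − 28) for D = 29 to 31
- letrozole = D

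| Day of sample | Ribociclib doses | Letrozole doses |
|---|---|---|
| before first dose | 0 | 0 |
| 7 | 7 | 7 |
| 14 | 14 | 14 |
| 21 | 21 | 21 |
| 28 | 21 | 28 |
| 30 | 21 + 2 = 23 | 30 |
| 31 | 21 + 3 = 24 | 31 |

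If the biopsy precedes that day's dose, the ribociclib counts for Days 28, 30 and 31 are 21, 22 and 23. These are maxima; a sample earlier in the window has seen less. A Day 28 sample also falls at the end of the ribociclib week off.

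**2. Text that might separate the samples**

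- Collection text (Synopsis, Section 4.1, Table 7-1 footnote 2): acknowledges that the window runs into treatment, but gives no analysis rule.
- Classification (Section 7.2.1, Table 7-2): places window tissue with pre-treatment or Screening tissue.
- Analysis set (Section 10.1): no timing condition.
- Analysis text (Section 10): descriptive statistics and exploratory modelling, with no flag, exclusion, stratification or sensitivity analysis by timing.

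The only classification visible is therefore the one that groups exposed with untreated tissue.

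**3. Why no bias figure is given**

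Let f be the share of baseline samples taken on treatment and r the share of the true pre-to-progression change already present in them. The value of r may be negative if the early effect runs the other way. If the late-sampled patients are otherwise like the rest, then

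observed mean change / true mean change = 1 − f × r.

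The documents give neither f nor r. With purely assumed values:

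- f = 0.10, r = 0.25: 1 − 0.025 = 0.975
- f = 0.50, r = 1.00: 1 − 0.50 = 0.50
- f = 0.30, r = −0.50: 1 + 0.15 = 1.15

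The ratio can fall on either side of 1 and be trivial or large, so neither size nor direction can be stated.

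**The case against.** The strongest reply is that the rule may exist where we cannot see it. The SAP and stand-alone plans were not supplied. Section 7.2.4, to which Table 7-1 refers for tissue collection, does not appear in the text; the headings on either side of 7.2.3 are redacted; and Section 10 is cut by redaction. This stands. A reader might infer that the plan has no timing rule, but the documents support only that none is visible. What remains is the label in Section 7.2.1, which an analysis plan using the same term would inherit.

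It can also be said that Screening in the tables is a visit name, that the window is disclosed, and that late samples can probably be identified from the requisition forms and parent-study dosing data. All fair. Disclosing when tissue may be taken does not say how it will be analysed, though, and being able to identify the samples is what makes the fix cheap.

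Three stronger readings are tempting and should be resisted:

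- *Two different window start dates.* Table 7-2 counts from study, and the Glossary defines enrollment as "Point/time of patient entry into the study; the point at which informed consent must be obtained". In context, next to a reference to pre-treatment collection and beside the Synopsis, Section 4.1, Table 7-1 and Section 7.2.1, the table plainly means the first month on treatment. The wording is only loose.
- *A quantified bias.* Any percentage rests wholly on assumed f and r, and no visible passage specifies a mean change as the summary.
- *Pre-dose samples must be the main analysis.* Restricting to them shifts the mix towards archival tissue, some of it from the primary site. Which set leads in exploratory work is a matter of judgement.

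**Conclusion.** The point holds as a minor one. The protocol classes fresh tissue with up to 21 to 24 ribociclib and 28 to 31 letrozole doses behind it as pre-treatment, and no visible rule separates it from untreated tissue in the exploratory expression and PDL-1/CD8 pre/post and predictor analyses. This is more than missing detail, because the stated classification, if followed, gives a worse contrast than one based on collection date.

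The dose range assumes uninterrupted dosing, a 28- to 31-day month and sampling at the end of the window. How many samples fall in the window is not stated; as it is a fallback, they may be few. There is no hypothesis test or sample size that this could undermine. If the SAP already classifies tissue by collection date, only the wording of Section 7.2.1 needs attention.

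**What to change.** In Section 7.2.1 or the SAP:

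1. Define pre-treatment tissue as tissue collected before the first dose of study treatment, and class fresh tissue taken after it as early on-treatment. Use the actual collection date, not the shipment date, so that archival tissue collected before the first dose stays pre-treatment.
2. Keep the one-month window, and keep early on-treatment samples for DNA mutation calls.
3. Report the expression and PDL-1/CD8 pre/post analyses and the baseline-predictor analysis on pre-dose samples alongside all samples.
4. Give the number of early on-treatment samples, the doses taken before each, and tissue source (fresh or archival, primary or metastatic) for both sets.

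As an editorial matter only, Table 7-2 should count the month from the start of treatment.

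The cost is a wording change and one variable derived from the collection date and the parent-study dosing dates. No procedure is added. The downside is that the pre-dose set is smaller and holds a larger archival share. With equal variances, its standard error rises by a factor of 1/√(1 − f): 1.05, 1.12 or 1.20 if the share set aside is an assumed 10%, 20% or 30%. Showing both sets with their tissue source lets the reader weigh exposure against source and precision.
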